6.4. Study Intervention Compliance

Study intervention will be self-administered and/or administered by designated study site personnel when the participant visits the site or is visited at home. Visits to the study site are indicated in the Schedule of Activities:

- For the main study:
 - Visiting the site is required on Days 1, 2, and 28. All other visits as indicated in the Schedule of Activities may either be performed at the site or by designated study site personnel who visits the participant at home. Between on-site visits, administration of study intervention will either be at home (including remote supervision of study intervention intake, if feasible) or participants may come to the site. MDs need to be taken approximately at the same timepoint every day.
- For the PK substudy:
 - Participants will remain at the site during the first 12 hours on Days 1 and 28. Visiting the site is required on Day 2 and Day 3. All other visits (Day 29 and Day 32) may either be performed at the site or by designated study site personnel who visits the participant at home.

Study intervention will be administered orally, and date/time of study intervention intake will be recorded by the participant in a diary.

When the participant visits the site, study intervention will be administered by designated study site personnel who will check the participant's mouth to confirm that the dose was swallowed. The date and time of each dose administered in the study site will be recorded in the source documents for on-site administration and recorded in the CRF. The intake of study intervention and study participant identification will be confirmed at the time of dosing by a member of the study site personnel other than the person administering the study intervention.

When participants self-administer study intervention at home, compliance with study intervention will be assessed as indicated in the Schedule of Activities. Administration of study intervention will either be at home (including remote supervision of study intervention intake, if feasible) or participants may come to the site (also see Section 8, Study Assessments and Procedures).

Participants will receive instructions on compliance with study intervention administration on Day 1. During the study, the investigator or designated study site personnel will be responsible for providing additional instruction to reeducate any participant who is not compliant with taking the study intervention.

Compliance will be assessed by counting returned tablets and review of the diary during the site or home visits and documented in the source documents and CRF. Deviation(s) from the prescribed dosage regimen should be recorded in the CRF.

The number of study intervention tablets dispensed will be recorded and compared with the number returned. A record of the number of study intervention tablets dispensed to and taken by each participant must be maintained and reconciled with study intervention and compliance records. Intervention start and stop dates, including dates for intervention delays and/or dose reductions will also be recorded in the CRF.

6.5. Dose Modification

Not applicable.

6.6. Continued Access to Study Intervention After the End of the Study

Participants will be instructed that study intervention will not be made available to them after they have completed/discontinued study intervention.

6.7. Treatment of Overdose

For this study, any dose of JNJ-64281802 greater than the assigned daily dose within a 24-hour time period (Table 2) will be considered an overdose. The sponsor does not recommend specific treatment for an overdose.

In the event of an overdose, the investigator or treating physician should:

- Contact the Medical Monitor immediately.
- Evaluate need to discontinue study intervention in consultation with the Medical Monitor.
- Closely monitor the participant for AE/SAE and laboratory abnormalities until JNJ-64281802 can no longer be detected systemically (at least 46 days).
- Document the quantity of the excess dose as well as the duration of the overdosing in the source documents and the CRF.

Decisions regarding dose discontinuation will be made by the investigator in consultation with the Medical Monitor based on the clinical evaluation of the participant.

6.8. Concomitant Therapy

Prestudy therapies administered up to 14 days before first dose of study intervention must be recorded at screening.

Concomitant therapies must be recorded in the CRF throughout the study from the screening visit until the last study-related activity, or until the participant has been deemed lost to follow-up after demonstration of due diligence of follow-up efforts.

In case any comedications are used, the dose and dosing regimen must be recorded in the Concomitant Therapy Section of the CRF. For any concomitant therapy given as a treatment for a new condition or a worsening of an existing condition (relative to the moment of signed ICF), the condition must be documented in the Adverse Event Section of the CRF.

The following medications other than the study intervention are allowed during (a part of) the study:

- The investigator may permit the use of paracetamol/acetaminophen from 3 days before first dose of study intervention until the last PK sample has been taken at ≤3 x 500 mg per day, and ≤3 grams per week. In case paracetamol/acetaminophen is used, the date and time of dosing, the indication, the dose, and the dosing regimen must be recorded in the Concomitant Therapy Section of the CRF. In order to minimize the antipyretic effects of paracetamol/acetaminophen on body temperature outcome readings, participants are recommended not to take paracetamol/acetaminophen within 4 hours before the next body temperature measurement, except those with high fever (≥39°C). In this case, the body temperature before taking paracetamol/acetaminophen, the dose taken, and the body temperature one hour after taking paracetamol/acetaminophen should be recorded in the daily dairy. In addition, the Medical Monitor should be informed about this occurrence.
- Stable HRT (ie, same dose and not starting or stopping HRT for 2 weeks before first dose of study intervention until the end of the study) in postmenopausal women is allowed. It should be noted that JNJ-64281802 may affect the effectiveness of HRT agents when coadministered. The use of HRT must be recorded in the Concomitant Therapy Section of the CRF. Applicable procedures and treatment guidance based on package inserts should be respected.

Other co-medication allowed include the following:

- H₁ receptor antagonists (with exception of mizolastine), topical corticosteroids, or antipruritic agents in the recommended dose scheme.
- H₂ receptor antagonists.
- The use of antiemetics in case of severe nausea.

For vaccinations:

- Participants will be allowed to receive an authorized/licensed COVID-19 vaccine throughout this study (see Appendix 4: COVID-19 Appendix), including attenuated COVID-19 vaccines and boosters.
- Other licensed live attenuated vaccines are not allowed from 28 days before first dose of study intervention until 90 days after last dose of study intervention. Furthermore, other licensed (not live) vaccines, are disallowed from 7 days before first dose of study intervention until 90 days after last dose of study intervention.

• Any prior vaccinations against DENV virus are not allowed until 90 days after last dose of study intervention. Vaccinations against all other flaviviruses are not allowed from 28 days before first dose of study intervention until 90 days after last dose of study intervention.

Participants must not use any immunosuppressive corticosteroids (excluding topical and nasal) or immunosuppressive drugs from 28 days before first dose of study intervention until 28 days after last dose of study intervention. An immunosuppressive dose of corticosteroids is defined as ≥ 10 mg prednisone equivalent per day for ≥ 14 days. In case immunosuppressive corticosteroids or immunosuppressive drugs are used, the date and time of dosing, the indication, the dose, and the dosing regimen must be recorded in the Concomitant Therapy Section of the CRF.

Participants must not use any anticoagulant medication or NSAIDs including aspirin, from screening until the last study visit. Aspirin and NSAIDs can interfere with the ability of the blood to clot. It is not anticipated that any participants will have severe DENV infection with bleeding problems, however, it is still recommended to avoid these drugs. The investigator may recommend paracetamol/acetaminophen or an equivalent at doses described above.

Use of any strong CYP3A4 inhibitors, strong CYP3A4 inducers, substrates for CYP3A4 with a narrow therapeutic index, or sensitive BCRP substrates from 7 days before first dose of study drug until 28 days after last dose of study drug is not permitted. In case any of these inhibitors or substrates are used, the date and time of dosing, the indication, the dose, and the dosing regimen must be recorded in the Concomitant Therapy Section of the CRF.

Refer to 10.10 Appendix 10: Examples of Disallowed Medications for examples of such disallowed medications.

The sponsor must be notified in advance (or as soon as possible thereafter) of any instances in which prohibited therapies are administered.

7. DISCONTINUATION OF STUDY INTERVENTION AND PARTICIPANT DISCONTINUATION/WITHDRAWAL

7.1. Participant Discontinuation Criteria

A participant's study intervention must be discontinued if:

- The participant withdraws consent to receive study intervention.
- The investigator believes that for safety reasons or tolerability reasons (eg, AE) it is in the best interest of the participant to discontinue study intervention.
- The participant becomes pregnant.
- As baseline (Day 1) laboratory results will not be available at randomization, any participant who reports with 2 or more ≥ Grade 2 laboratory abnormalities for ALT, AST, creatinine, lipase, absolute neutrophil count, platelet count, or hemoglobin at baseline, must be discontinued. Discontinuation of study intervention should only occur after a confirmatory retesting result and if deemed clinically significant by the investigator.

- Noncompliance with study intervention administration occurs, defined as missing a LD, 2 consecutive MDs, or 2 nonconsecutive MDs within a week (judged case-by-case after discussion between the Sponsor and investigator).
- In case of abnormal liver tests as outlined in 10.11 Appendix 11: Liver Safety: Suggested Actions and Follow-up Assessments and Section 7.1.2 Participant Stopping Criteria due to Liver Chemistry.

If a participant discontinues study intervention prematurely for any reason other than withdrawal of consent before the end of the double-blind prophylactic dosing phase, a withdrawal visit should be scheduled as soon as possible after the decision for discontinuation, followed by a follow-up visit, which is preferably scheduled 13 to 17 days after the last dose study intervention intake, if the condition of participant allows (see Section 1.3.2.4, Discontinuation From Study Intervention or Study). Blood sample should be collected at the withdrawal and follow-up visits for immune assessments, viral analysis, viral genome sequencing, and safety assessments (at the follow-up visit, safety assessments should occur at the discretion of the investigator).

Study intervention assigned to the participant who discontinued study intervention may not be assigned to another participant. Additional participants will be entered to ensure the protocol-specified number of participants complete the study.

Please refer to Appendix 4: COVID-19 Appendix for guidance on study conduct during the COVID-19 pandemic.

7.1.1. Participant Stopping Criteria due to DENV infection

In addition to the discontinuation criteria outlined in Section 7.1 above, HHCs who develop DENV-associated clinical warning signs and symptoms (according to Appendix 3: WHO Clinical Classification of Dengue Disease) during the study and require hospitalization will be withdrawn from study intervention. The participant will perform a withdrawal and safety follow-up visit as described in Section 7.1, Discontinuation of Study Intervention.

The participant will receive medical care according to local standards. Hospitalization is classified as SAE and should be reported accordingly (see Section 8.3, Adverse Events, Serious Adverse Events, and Other Safety Reporting).

7.1.2. Participant Stopping Criteria due to Liver Chemistry

Stopping of study intervention for abnormal liver tests is required by the investigator when a participant meets one of the conditions outlined in 10.11 Appendix 11: Liver Safety: Suggested Actions and Follow-up Assessments, after consultation with the sponsor, or in the presence of abnormal liver chemistries not meeting protocol-specified stopping rules if the investigator believes that it is in best interest of the participant.

7.1.3. Study Pausing Criteria

If significant safety concerns arise following administration of study intervention (and a specific set of study pausing criteria have been met), further randomization and dosing of participants may be paused.

The reasons for pausing the study are listed below. The list only applies for events that are considered by the investigator to be related to study intervention and unrelated to dengue disease or an associated infection (eg, COVID-19).

- Death of a participant, considered related to study intervention or if the causal relationship to the study intervention cannot be excluded; OR
- Three or more participants at one study site or six or more participants at all study sites experience a ≥Grade 3 unsolicited AE of the same type (as per medical judgment of the sponsor) that is considered related to study intervention;

Note: An AE report based on a \geq Grade 3 laboratory abnormality will only be considered if the laboratory abnormality is clinically significant and persistent (upon repeated testing) per the investigator. Elevations of total cholesterol will not be considered.

OR

• Any safety findings that in the opinion of the sponsor or the IDMC warrants pausing (or cessation) of dosing.

To enable a prompt response to a situation that could trigger the study pausing criteria, the investigator should notify the sponsor's medical monitor (or designee) immediately and no later than 24 hours after becoming aware of any ≥Grade 3 unsolicited AE considered related to study intervention (and update the CRF with relevant information on the same day the AE information is collected). A thorough analysis of all reported ≥Grade 3 unsolicited AEs will initially be carried out by the sponsor's medical monitor (or designee). Based on the available data, the sponsor's medical monitor (or designee) will determine whether a safety data review by the IDMC is warranted, to assess whether the study pausing criteria are met.

If the IDMC judges that the study pausing criteria have been met, the IDMC will recommend to either pause the study or to implement modifications to the study conduct and/or to the safety assessments. If safety concerns would occur only with the HDR, the IDMC may recommend to pause randomization and dosing in the HDR group but continue randomization and dosing in the LDR and placebo groups.

In case the IDMC recommends a study pause, all sites/investigators will be notified immediately of the pause by the sponsor's medical monitor (or designee).

In case a safety data review by the IDMC was triggered because three or more participants at one study site or six or more participants at all study sites experienced a ≥Grade 3 unsolicited AE of the same type (as per medical judgment of the sponsor) that is determined to be related to study intervention, the IDMC will indicate the conditions under which it requires further notification and review of the subsequent similar AEs.

At any point during the study, the IDMC has the authority to recommend modifications to the study conduct and/or to the safety assessments to the Sponsor Committee to ensure the safety of enrolled participants. The IDMC can recommend to the Sponsor Committee to halt a dose arm or to pause or stop the study due to safety concerns.

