10.7.2. Attribution Definitions

Assessment of Causality

The causal relationship to study intervention is assessed by the investigator. The following selection must be used to assess all AEs.

Related

There is a reasonable causal relationship between study intervention administration and the AE.

Not Related

There is not a reasonable causal relationship between study intervention administration and the AE.

The term "reasonable causal relationship" means there is evidence to support a causal relationship.

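### The numeric pausing trigger in Protocol 7.1.3 counts only unsolicited AEs, so a cluster of drug-related Grade 3 rash recorded as rash cannot meet it (minor gap, cheap to close)

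*Protocol*

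**What the plan says.** Protocol 7.1.3 lists three grounds for pausing randomization and dosing, under the condition: "The list only applies for events that are considered by the investigator to be related to study intervention and unrelated to dengue disease". Events due to an accompanying infection such as COVID-19 are left out in the same way.

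- **Criterion 1** is a death.
- **Criterion 2** is the only one with a number. It is met when three or more participants at one site, or six or more across sites, "experience a ≥Grade 3 unsolicited AE of the same type", considered related to study intervention.
- **Criterion 3** is a matter of judgment: "Any safety findings that in the opinion of the sponsor or the IDMC warrants pausing" or stopping of dosing.

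The steps around criterion 2 have the same scope. The investigator must notify the medical monitor within 24 hours of a related ≥Grade 3 unsolicited AE. The monitor then analyses the ≥Grade 3 unsolicited AEs and "will determine whether a safety data review by the IDMC is warranted". The paragraph on what follows a count-triggered review again refers to participants who "experienced a ≥Grade 3 unsolicited AE of the same type". Sections 8.3.1 (notice) and 10.6.6 (review triggered by the monitor) repeat the restriction.

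Section 8.3.2 defines solicited AEs as a predefined list and unsolicited AEs as everything the participant is not specifically asked about. Rash is on the solicited list (Table 3).

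**The concern.** Section 2.3.1 names rash as a risk of the drug: two Grade 2 events in the multiple-dose part of the first-in-human study, both judged very likely related. No other entry in that risk table is a reaction seen in people and attributed to the drug. Rash also has its own management appendix (10.2). The numeric rule therefore covers any single unsolicited reaction and leaves out the one reaction already linked to the drug.

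At stake is speed. Six related, non-serious Grade 3 events of one unsolicited type would each prompt a 24-hour notice and together would meet criterion 2. Six related, non-serious Grade 3 rashes recorded as rash would do neither. They would reach the IDMC through its periodic review or because someone judged them worth referring.

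**Working it through.** **Scope check.** This is a reading of the text; the plan states no operating characteristic for the pausing rule that could be reproduced.

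| Step | Events covered | Place |
|---|---|---|
| Count, 3 at one site or 6 overall | ≥Grade 3 unsolicited | 7.1.3 |
| 24-hour notice to the medical monitor | ≥Grade 3 unsolicited | 7.1.3, 8.3.1 |
| Medical monitor's analysis | ≥Grade 3 unsolicited | 7.1.3, 10.6.6 |
| Follow-up after a count-triggered review | ≥Grade 3 unsolicited | 7.1.3 |
| Rash | solicited | 8.3.2, Table 3 |

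No text moves a drug-related rash into the unsolicited class. If N participants have related, non-dengue Grade 3 rash recorded as rash, their contribution to the count is 0 for every N.

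**Dependence on the recorded term.** Section 10.7.5 prefers a diagnosis to its signs where one can be given, and 10.2 requires a biopsy for Grade 3 rash. A reaction entered under a diagnosis might be treated as unsolicited and counted. The documents do not settle this, so the same reaction could count at one site and not at another.

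**Contrast with liver events.** Section 10.11.2 requires a liver event to be reported to the sponsor within 24 hours. Section 10.2 sets no such deadline for rash.

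**Phase 1 figure.** 2/47 = 4.3% with Grade 2 related rash; exact 95% CI 0.5% to 14.5%. That study was placebo-controlled, so the 47 may include placebo recipients. The events arose at 400 and 560 mg daily. That is above the maintenance doses here (150 and 50 mg), though the high-dose loading is 2 × 400 = 800 mg per day for two days.

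**Illustration only.** The documents give no Grade 3 rash rate, so the rates below are assumptions, with one rate applied to both active arms. Planned enrolment of 1,250 to 1,850 at 1:1:1 puts 1,250 × 2/3 = 833 to 1,850 × 2/3 = 1,233 on active drug. The study stopped at 21 of 36 primary events. If enrolment scaled in proportion (a further assumption), that becomes 833.3 × 21/36 = 486 to 1,233.3 × 21/36 = 719. With X binomial(n, p), the chance of six or more is:

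| Assumed rate p | n = 833 to 1,233 | n = 486 to 719 |
|---|---|---|
| 0.2% | 0.007 to 0.040 | 0.0005 to 0.004 |
| 0.5% | 0.241 to 0.581 | 0.037 to 0.155 |
| 1% | 0.839 to 0.984 | 0.359 to 0.724 |
| 2% | 0.999 to >0.9999 | 0.924 to 0.996 |

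The answer runs from negligible to near certain with the assumed rate, so the table cannot show that a cluster was likely. It shows only that six events is a reachable number at rates around 0.5% to 1%. The three-at-one-site limb is not computed because the documents give no site count.

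**The case against.** The best defence is that solicited events are by design the signs of dengue. Section 10.2 says dengue rash and drug rash may be impossible to tell apart, and 6.3 allows virologic data to be kept from investigators. A count that depends on attribution is least reliable for such events, so managing rash under its own protocol is defensible. Part of this stands: including rash would bring in some events whose attribution is uncertain. It does not explain leaving out a rash that the investigator has already judged related to the drug and unrelated to dengue, which is all that criterion 2 would admit.

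The second defence is the other safeguards, and it largely stands as to weight.

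- Under 10.2, Grade 3 rash means permanent discontinuation without rechallenge, withdrawal from the study, dermatology referral and biopsy. Photographs go to a server that IDMC members can open.
- Serious rash is reported as an SAE within 24 hours (8.3.1).
- SAP 5.7.4 describes regular unblinded IDMC review that includes AEs, and SAP 5.6.2 tabulates solicited AEs by arm.
- Under 10.6.6, an event that the investigator or study physician judges significant or unexpected leads to unblinded IDMC review at any time, whether solicited or not.
- Criterion 3 can still apply, and "The IDMC can recommend to the Sponsor Committee to halt a dose arm or to pause or stop the study" at any point.
- The numeric route is itself partly discretionary, because the monitor decides whether IDMC review is warranted.

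A reader might also infer that the lead-in empties the death criterion. The criterion covers a related death "or if the causal relationship to the study intervention cannot be excluded", while the lead-in requires relatedness, which in 10.7.2 "means there is evidence to support a causal relationship". The documents do not support treating this as a defect. The specific death wording can naturally be read as qualifying the general lead-in, and 10.6.6 sends every death to the IDMC whatever its cause. Nor is criterion 3 clearly tied to the investigator's attribution, since it names its own assessors.

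**Conclusion.** The point holds as a minor gap in the text. A cluster of non-fatal, drug-related, non-dengue Grade 3 rash recorded as rash meets no numeric pausing trigger and prompts neither the 24-hour notice nor the monitor's pausing analysis, unless the events are serious or are recorded under another term. What is missing is one prompt, countable route between IDMC meetings.

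A reader might go further and infer that such rashes would escape oversight, or that a cluster was likely. The documents support neither. Several other routes lead to the IDMC, and the unredacted text reports no Grade 3 rash in the first-in-human study. No efficacy estimate or conclusion is affected. The study ended on 02 October 2024 for portfolio reasons and not on safety grounds (SAP 1), so the value now lies in any later protocol that reuses this wording.

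The conclusion rests on Table 3 governing how rash is classified. The IDMC charter is not among the documents and might already contain a rash rule.

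**What to change.** Replace ≥Grade 3 unsolicited AE by **≥Grade 3 unsolicited AE or ≥Grade 3 rash** in:

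- criterion 2 of 7.1.3;
- the notice, analysis and follow-up sentences of 7.1.3;
- the matching sentences of 8.3.1 and 10.6.6.

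Keep the existing conditions that the event is judged related to study intervention and unrelated to dengue or an associated infection. Leave the lead-in and the death criterion as they are. Mirror the phrase in the IDMC charter if it has no equivalent rule.

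The cost is one phrase in three sections. Rash is already graded and recorded and the IDMC is already unblinded, so no new data are needed and the sample size does not change. The downside is an occasional extra notification or IDMC review, including for rashes whose attribution is uncertain because dengue also causes rash.
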